7.6 Early study termination by the sponsor

The study can be terminated by Novartis at any time for any reason. This may include reasons related to the benefit/ risk assessment of participating in the study, practical reasons (including slow enrollment), or for regulatory or medical reasons. Should this be necessary, subjects must be seen as soon as possible and treated as a prematurely discontinued subject. The investigator may be informed of additional procedures to be followed in order to ensure that adequate consideration is given to the protection of the subject's interests. The investigator will be responsible for informing IRBs/IECs of the early termination of the trial.

8 Procedures and assessments

8.1 Assessment schedule

Subjects should be seen for all visits/assessments as outlined in the [Assessment schedule](#) or as close to the designated day/time as possible.

Missed or rescheduled visits should not lead to automatic discontinuation. Subjects who prematurely discontinue the study for any reason should be scheduled for a visit as soon as possible, at which time all of the assessments listed for the final visit will be performed. At this final visit, all dispensed investigational product should be reconciled, and the adverse event and concomitant medications recorded on the CRF.

Table 8-1 Assessment schedule

Epoch	Screening				Treatment													
Visit Name	Screening ¹⁴		Baseline ¹⁵		Up-Titration 50 mg bid (Days 1 to 7)		Up-Titration 100 mg bid (Days 8 to 14)		Treatment									
Visit Numbers ¹	1	2	3 ¹⁶	4	101	102	103	104	105	106	107	108	109	110	111	112	113	114
Days	-28 to -12	-14 to -11	-13 to -10	-3 to -1	1	4 ±1	8 ±1	11 ±1	15 ±1	18 ±1	22 ±1	25 ±1	29 ±1	32 ±1	36 ±1	39 ±1	43 ±1	46 ±1
Time (post-dose)	-	-	-	-	-	-	-	-	0h	2h ±1	-	-	-	0h	2h ±1	-	-	-
Informed consent	X																	
Commercially Confidential Information	Commercially Confidential Information																	
Demography	X																	
Body Weight	X																	
Body Height	X																	
Body Temperature	X			X	X ³													
Blood Pressure and Pulse Rate	X			X	X ³													
Physical Examination	X			X														
Medical history/current medical conditions	X																	
reduce / cease cocaine use ¹⁷				X														
Amount spent on cocaine				X									X					
TLFB cocaine	X																	
TLFB alcohol	X																	
Urine drug screen	X	X	X	X	X	X	X	X	X	X	X	X	X	X	X	X	X	X
Commercially Confidential Information	Commercially Confidential Information																	
Hepatitis screen	S																	
Hematology	X			X									X					

Epoch	Treatment																Follow up				
Visit Name	Treatment																Follow up				
Visit Numbers ¹	115	116	117		118	119	120	121	122	123	124	125	126	127	128	199	201	202	203		
Days	50 ±1	53 ±1	57 ±1		60 ±1	64 ±1	67 ±1	71 ±1	74 ±1	78 ±1	81 ±1	85 ±1	88 ±1	92 ±1	95 ±1	98 ±1	99 ±1	102 ±1	106 ±1		
Time (post-dose)	-	-	0h	2h ±1	-	-	-	-	-	-	-	-	-	-	-	0h	2h ±1	-	-	-	
Informed consent																					
Commercially Confidential Information																					
Demography																					
Body Weight																					
Body Height																					
Body Temperature	X ³																				
Blood Pressure and Pulse Rate	X ³																				
Physical Examination																					
Medical history/current medical conditions																					
reduce / cease cocaine use ¹⁷																					
Amount spent on cocaine				X												X					
TLFB cocaine	X																				
TLFB alcohol	X																				
Urine drug screen	X	X	X	X	X	X	X	X	X	X	X	X	X	X	X			X	X	X	
Commercially Confidential Information																					
Hepatitis screen																					
Hematology			X													X					
Blood chemistry			X													X					
Urinalysis			X													X					
Pregnancy test ⁴			X ⁶				X ⁶					X ⁶				X ⁶					
ECG evaluation ⁷			X	X												X	X				

Epoch	Follow up	
	Follow up	EOS
Visit Name		
Visit Numbers ¹	204	299
Days	112 ±1	113 ±3
Time (post-dose)	-	-
Informed consent		
Commercially Confidential Information		
Demography		
Body Weight		X
Body Height		
Body Temperature	X ³	X ³
Blood Pressure and Pulse Rate	X ³	X ³
Physical Examination		X
Medical history/current medical conditions		
reduce / cease cocaine use ¹⁷		
Amount spent on cocaine		X
TLFB cocaine	X	
TLFB alcohol	X	
Urine drug screen	X	
Commercially Confidential Information		X
Hepatitis screen		
Hematology		X
Blood chemistry		X
Urinalysis		
Pregnancy test ⁴		X ⁶
ECG evaluation ⁷		X
HIV screen		

Epoch	Follow up	
	Follow up	EOS
Visit Name		
Visit Numbers ¹	204	299
Days	112 ±1	113 ±3
Time (post-dose)	-	-
Concomitant therapies ⁸	X	X
Drug administration record		
Medication patient diary ⁹		
Commercially		
Confidential		
Information		
C-SSRS ¹⁰	X	X
PK blood collection ¹¹		
Commercially Confidential Information		
Adverse Events ¹²	X	X
Serious Adverse Events ¹³	X	X
Study completion information		X

- ¹ Visit structure given for internal programming purpose only.
Commercially Confidential Information
- ³ Assessment to be done once per week, during one of the visits when urine sample is collected.
- ⁴ Assessment for females patients only.
- ⁵ Serum pregnancy test
- ⁶ Urine pregnancy test
- ⁷ On PK days , assessment to be done after post dose PK sample
- ⁸ Record includes: Positive Reinforcement
- ⁹ Medication compliance to be assessed at least once per week
- ¹⁰ Assessment to be done at every visit
- ¹¹ Pk samples collected in the morning at predose and 2 ± 1 hours post-morning dose
- ¹² AEs to be collected from signed ICF up to study completion visit (EOS)
- ¹³ SAEs to be collected from signed ICF up to 30 days following study completion visit (EOS)
- ¹⁴ If considered appropriate by the investigator, screening assessments may be carried out on two separate days.
- ¹⁵ If considered appropriate by the investigator, baseline assessments may be carried out on two separate days.
- ¹⁶ Visit 3 should take place 1-3 days after visit 2.
- ¹⁷ Subjects should be asked about their goals to cease/reduce cocaine use. Guidance is provided in the SOM.

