7.1 Study completion and post-study treatment

Each subject will be required to complete the study in its entirety and thereafter no further study treatment will be made available to them.

Study completion is defined as when the last subject completes their Study Completion visit, and any repeat assessments associated with this visit have been documented and followed-up appropriately by the Investigator, or in the event of an early study termination decision, the date of that decision.

All randomized and/or treated subjects will have a safety follow-up call conducted 14 days after last administration of study treatment. The information collected is kept as source documentation. All SAEs reported during this time period must be reported as described in [Section 9.2](#) and the Site Operations Manual. Documentation of attempts to contact the subject should be recorded in the source documentation.

Continuing care should be provided by investigator and/or referring physician based on subject availability for follow-up. This care may include:

- promote compliance for the visits schedule for urine samples collection
- promote compliance for data entry in TLFB cocaine , as well as TLFB alcohol

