7.2 Discontinuation of study treatment

Discontinuation of study treatment for a subject occurs when study treatment is stopped earlier than the protocol planned duration. Discontinuation of study treatment can be decided by either the subject or the investigator.

Discontinuation of study treatment and patient withdrawal will be at the discretion of the Investigator, under the following circumstances:

- Moderate and persistent (>24 hours) CNS related AEs, i.e.. behavioral effects and/or neurological adverse effects, in the opinion of the Investigator as suspected to be related to AFQ056 study medication
- Missed > 6 consecutive visits
- Missed > 7 consecutive doses of study medication during the fixed-dose treatment period or a total of more than 14 cumulative doses at any time during the study
- Use any of prohibited treatment

* If a liver or renal event occurs, follow guidelines outlined in [Appendix 2](#) regarding discontinuation of study treatment.

Study treatment **must be** discontinued under the following circumstances:

- Subject/guardian decision - subjects may choose to discontinue study treatment for any reason at any time.
- The investigator believes that continuation would negatively impact the safety of the subject or the risk/benefit ratio of trial participation.
- Any protocol deviation that results in a significant risk to the subject's safety.
- Pregnancy (see [Section 8.6](#) (Safety) and [Section 9.6](#) (Pregnancy reporting)).
- Severe withdrawal syndrome or need for detoxification

For all discontinued patients, the follow-up period is to be followed, where possible.

Patients, who discontinue study treatment must NOT automatically be considered withdrawn from the study. Patients who discontinue study treatment before completing the study, and those who prematurely withdraw from the study for any reason, must be scheduled for a visit approximately 1 week after the last dose of study medication, at which time all of the assessments listed for the final visits (End of Study visit) must be performed (see [Assessment schedule](#)).

After study treatment discontinuation, at a minimum, the following data should be collected at clinic visits or via telephone/email contact:

- new / concomitant treatments
- adverse events/Serious Adverse Events

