9.1 Adverse events

An adverse event (AE) is any untoward medical occurrence (i.e., any unfavorable and unintended sign [including abnormal laboratory findings], symptom or disease) in a subject after providing written informed consent for participation in the study until the end of study visit. Therefore, an AE may or may not be temporally or causally associated with the use of a medicinal (investigational) product.

In addition, all reports of intentional misuse and abuse of the study treatment are also considered an adverse event irrespective if a clinical event has occurred. See [Section 9.5](#) for an overview of the reporting requirements.

The occurrence of adverse events must be sought by non-directive questioning of the subject at each visit during the study. Adverse events also may be detected when they are volunteered by the subject during or between visits or through physical examination finding, laboratory test finding, or other assessments.

Abnormal laboratory values or test results constitute adverse events only if they fulfill at least one of the following criteria:

- they induce clinical signs or symptoms,
- they are considered clinically significant,
- they require therapy.

Clinically significant abnormal laboratory values or test results should be identified through a review of values outside of normal ranges/clinically notable ranges, significant changes from baseline or the previous visit, or values which are considered to be non-typical in patients with underlying disease. Investigators have the responsibility for managing the safety of individual subject and identifying adverse events. Alert ranges for liver and kidney related events are included in [Appendix 1](#) and [Appendix 2](#), respectively.

For all completed scales/questionnaire described below, the Investigator will be required to review and examine responses which may indicate potential AEs or SAEs. The investigator should review not only the responses to the scale but also for any unsolicited comments written by the subject. If the occurrence of AEs or SAEs is confirmed, the physician should record the events as per instructions given in [Section 7](#). Investigators should not encourage the subjects to change the responses reported on the scale.

Adverse events should be recorded on the Adverse Events CRF under the signs, symptoms or diagnosis associated with them, and accompanied by the following information:

- AE severity grade (mild/moderate/severe):

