11.4.1 Primary Variable(s)

The primary variable is the proportion of cocaine use days during the treatment period (days 1-98).

For each patient, the proportion of cocaine use days will be calculated by dividing the number of days of cocaine use during the treatment period, i.e. 98 days for completers and number of days between Day 1 and day of last dose in case of premature discontinuation of study treatment. It is considered as a continuous variable with a normal distribution. The cocaine consumption will be recorded daily (Yes/No) using the TLFB during the entire study.

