### **1.4 Study design and treatment**

This is a randomized, subject and investigator blinded, parallel group, placebo-controlled study in approximately 60 patients with cocaine use disorder. The study consists of: about 17-day screening period followed by a 12-day baseline; a 98-day out-patient treatment period (14-day up-titration dose regimen followed by 84-day maintenance dose) and finally an end of study visit evaluation approximately 14-days after the last study drug administration. The total

duration for each patient in the study is up to approximately 20-weeks including screening and baseline. The study design is summarized in Figure 1.4-1 below.

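### The protocol gives conflicting rules on when collection of non-serious AEs ends for patients who stop treatment early

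*Protocol*

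**What the plan says.** Two places in the protocol end AE collection at the End of Study (EOS) visit. Footnote 12 to Table 8-1 reads: "AEs to be collected from signed ICF up to study completion visit (EOS". Section 9.1 defines an AE as an event occurring "after providing written informed consent for participation in the study until the end of study visit".

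For completers, Table 8-1 puts EOS at Day 113 with a window of 3 days either side, after treatment on Days 1 to 98. SAP section 1.4 describes "an end of study visit evaluation approximately 14-days after the last study drug administration".

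For patients who stop early, several rules stand next to each other:

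- Section 7.2 says that patients who stop treatment, and those who leave the study, "must be scheduled for a visit approximately 1 week after the last dose of study medication", with all EOS assessments done at that visit.
- Section 7.2 also says: "For all discontinued patients, the follow-up period is to be followed, where possible". It adds that stopping treatment is not automatically withdrawal, and that AEs and SAEs are the minimum to be collected afterwards by visit, telephone or email. It gives no end date.
- Section 8.1 says: "Subjects who prematurely discontinue the study for any reason should be scheduled for a visit as soon as possible". That sentence covers those who leave the study, not everyone who stops the drug.
- Section 7.1 gives all randomized or treated subjects a "safety follow-up call conducted 14 days after last administration of study treatment. The information collected is kept as source documentation". It then specifies onward reporting for SAEs only.

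For SAEs, section 9.2.2 runs reporting to 30 days after the last dose, while footnote 13 runs collection to 30 days after EOS.

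**The concern.** If the 1-week visit with EOS assessments counts as the study completion visit of footnote 12, a new non-serious AE in the second week off drug reaches the CRF for a completer but may not for a patient who stopped early. If the site instead follows the other sentences of section 7.2, the same event is collected. The protocol does not say which rule takes precedence, so two sites could treat identical patients differently, and each could point to the text.

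The AE table by treatment (protocol 11.5.2, SAP 7.2) counts subjects with events in each arm. It could then rest on observation windows that depend on whether the patient stopped, which happens after randomization and may be related to treatment.

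The same ambiguity affects scheduled measurements. EOS hematology, chemistry, ECG and C-SSRS would be read about 7 days off drug in some patients and about 15 days in others. Laboratory and ECG data are summarised, and C-SSRS data listed, by visit under a single EOS label.

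**Working it through.** The check is day arithmetic plus a comparison of the rules.

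**Inputs.** Last treatment day for completers: Day 98 (protocol 11.4.1: "The primary variable is the proportion of cocaine use days during the treatment period (days 1-98"). EOS: Day 113 ±3 (Table 8-1). EOS assessments after early stopping: about 7 days after last dose (7.2). Safety call: 14 days after last dose (7.1). SAE limits: 30 days after last dose (9.2.2) or 30 days after EOS (footnote 13).

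**1. Completer window.** EOS day minus last dose day: 113 − 98 = 15 days. This agrees with the SAP's approximate figure of 14 days. With the EOS window, 110 − 98 = 12 and 116 − 98 = 18. If the Day 98 visit also moves by its permitted 1 day, 110 − 99 = 11 and 116 − 97 = 19.

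**2. Early-stopper window for new non-serious AEs, by the rule a site follows.**

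| Rule treated as decisive | Days off drug | Ratio to 15 days |
|---|---|---|
| 1-week visit is EOS and closes collection (7.2 with footnote 12 and 9.1) | about 7 | 7/15 = 0.47 |
| 14-day call counts as AE collection (7.1) | 14 | 14/15 = 0.93 |
| Follow-up period completed after last dose (7.2) | up to 15 | up to 15/15 = 1.0 |

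On the first row the difference is 15 − 7 = 8 days. The ratio is 7/14 = 0.50 on the SAP's figure, and runs from 7/19 = 0.37 to 7/11 = 0.64 across the visit windows.

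**3. Does the literal text support the first row?** It can. The EOS column of Table 8-1 includes study completion information, and section 7.2 wants all EOS assessments at 1 week, so that visit can be taken for the study completion visit. Section 9.1 sends events after the protocol observation period to source documents, with only SAEs reported to the sponsor. Section 7.1 treats the 14-day call in the same way. Section 9.2.1 says all AEs go on the CRF, but section 9.1 has already limited what counts as an AE to the period before EOS.

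**4. Does the text force the first row?** No. Section 7.2 asks that certain assessments be done at 1 week; it does not say that AE collection ends there. It also asks for the follow-up period and for continued AE collection.

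**5. SAEs.** Under 9.2.2 the window is 30 against 30 days, a ratio of 1.0. Under footnote 13, with a 1-week EOS, it is 7 + 30 = 37 against 15 + 30 = 45 days, a ratio of 37/45 = 0.82. The two rules disagree, but neither halves SAE coverage.

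**6. Patients affected.** The documents give no clear rate of early stopping. If 10% to 30% stop, that is 3 to 9 of 30 patients per arm (0.10 × 30 = 3; 0.30 × 30 = 9). This range is an assumption, and nothing in the documents says how it would divide between the arms.

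**The case against.** The strongest reply is that section 7.2, read as a whole, does not shorten anything. It keeps patients who stop treatment in the study, asks for the follow-up period and requires AE collection afterwards. Section 7.1 adds a call at 14 days for everyone. SAEs are covered to 30 days after last dose, and section 9.1 requires a detected AE to be followed until it resolves or is judged permanent, so the event that led to stopping is not cut off. Section 7.4 speaks of a scheduled EOS visit still to come for patients who no longer attend. If that means calendar Day 113, a patient stopping on Day 30 would have 113 − 30 = 83 days off drug, longer than any completer.

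Much of this stands. A reader might infer that the plan halves off-drug AE follow-up in early stoppers. The documents do not support that as a statement of fact: it describes one reading, and only for new non-serious AEs. A reader might also infer that AE frequency on AFQ056 would be understated because more patients on active drug would stop for AEs. No stopping rate by arm is given, and the AE table counts subjects, so a patient who stopped for an AE is already counted in it. The SAP's registry AE tables still carry an unresolved choice between on-treatment and treatment-emergent events, so it is not known whether the second week off drug enters them.

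The reply does not remove the conflict. The follow-up period is asked for only where feasible, the continued AE collection has no end date, and the call is not tied to the AE CRF. A telephone call also yields no laboratory or ECG data. For patients who leave the study, sections 7.2 and 8.1 give different timings for the final visit.

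**Conclusion.** The passages conflict, and the point is minor. Under the protocol as written, the post-dose window for CRF capture of new non-serious AEs in an early stopper could be about 7 days or as long as a completer's 15 days (12 to 18), depending on which sentence the site follows. The short end assumes that the 1-week visit is taken as the study completion visit and that AEs from the 14-day call stay off the CRF. The long end assumes that the follow-up period is completed after the last dose.

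The consequence is an AE comparison whose observation windows could depend on stopping, together with EOS laboratory, ECG and C-SSRS readings taken at two different times off drug. The size and direction of any bias cannot be determined from the documents, and claims of halved safety follow-up or of an understated AE rate on AFQ056 go beyond them.

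**What to change.** Reconcile protocol 7.1, 7.2, 8.1, 9.1 and footnote 12 as follows:

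- Anchor the end of AE collection on the last dose, in the same way for every dosed patient who has not withdrawn consent. Section 7.3 bars further contact after consent withdrawal unless safety findings require it, so those patients stay outside the rule.
- State that the 1-week visit does not itself end AE collection.
- Enter non-serious AEs reported at the existing 14-day call on the AE CRF.
- Label laboratory, ECG and C-SSRS data from the 1-week visit as early termination rather than EOS in by-visit outputs.
- Align the SAE end date in 9.2.2 with footnote 13, and reconcile the final-visit timing in 7.2 and 8.1 for patients who leave the study.

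The cost is protocol wording, a CRF completion instruction and a few more AE entries. The call is already scheduled for every randomized or treated subject, so no new contact is needed.

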8.2 Informed consent procedures

Eligible subjects may only be included in the study after providing written (witnessed, where required by law or regulation), IRB/IEC-approved informed consent.

If applicable, in cases where the subject's representative gives consent (if allowed according to local requirements), the subject must be informed about the study to the extent possible given his/her understanding. If the subject is capable of doing so, he/she must indicate assent by personally signing and dating the written informed consent document or a separate assent form.

Informed consent must be obtained before conducting any study-specific procedures (e.g. all of the procedures described in the protocol). The process of obtaining informed consent must be documented in the subject source documents.

Novartis will provide to investigators a proposed informed consent form that complies with the ICH E6 GCP guideline and regulatory requirements and is considered appropriate for this study. The informed consent form will also include a section related to optional future research which will require a separate signature if the subject agrees to future research. The procedures set out in the main consent form concerning the storage, maintenance of privacy, and release of the data or specimens for the main study will also be adhered to for any future research. Any changes to the proposed consent form suggested by the investigator must be agreed to by Novartis before submission to the IRB/IEC.

Information about common side effects already known about the investigational drug can be found in the Investigator's Brochure (IB). This information will be included in the subject informed consent and should be discussed with the subject during the study as needed. Any new information regarding the safety profile of the investigational drug that is identified between IB updates will be communicated as appropriate, for example, via an Investigator Notification or an Aggregate Safety Finding. New information might require an update to the informed consent and then must be discussed with the subject.

Commercially Confidential Information

A copy of the approved version of all consent forms must be provided to the Novartis monitor after IRB/IEC approval.

Refer to the Site Operations Manual for a complete list of Informed Consent Forms included in this study.

